1.0 Objectives

The **primary aim** of this proposal is to use a **phase II randomized controlled trial** to compare the **intervention of a second regional anesthetic block (QL block) versus usual care** (single intraoperative QL block) to **increase the proportion of opioid-free pancreatic cancer survivors** at discharge after potentially curative surgery. The primary outcome measure will be the proportion of patients in each arm who are opioid-free at discharge and thus not requiring any opioids on their discharge prescription. **Both arms will include a standardized non-narcotic bundle** for pain control supplementation during hospital stay and upon discharge and previously published enhanced surgical recovery protocols, based on pancreatic leak risk.

PICO: In patients undergoing open pancreatectomy using general anesthesia with regional pain block (QL block with 72-hr liposomal bupivacaine) [**Patients**], can the placement of a 2nd QL block (on postoperative day 4) [**Intervention**] more effectively wean patients off opioids during the inpatient stay vs. usual care of QL block (both arms with low-dose IV-PCA with non-narcotic bundle) [**Control**]. The primary outcome measure will be the proportion of patients able to be opioid free on discharge prescriptions [**Outcome**].

Outcome Measures:

Primary:

- **Proportion of patients** totally free of opioids on discharge, requiring no opioid prescription.

Secondary:

- **Hospital Measures**
 - Total oral morphine equivalents (OME) mg – which arm is lower and what effect size difference
 - Cost [hospital charges x cost/charge ratio] and cost-benefit analysis
 - Patient Reported Outcomes for gastrointestinal surgery– MD Anderson Symptom Inventory (MDASI-GI) for Patient-Reported Outcomes
- **Discharge Measures**
 - Actual initial discharge pain prescription dosage/size [CDC recommendation is <200mg after surgery]
 - % patients with initial discharge Rx dosage/size total OME <200mg
 - % patients using opioids on POD 30
 - MDASI-GI in clinic visits
 - % pts using opioids at POD 90
 - Total OME for first 30 days and first 90 days [inpatient + outpatient]
 - 6-mo and 1-yr follow-up – pts and family free of opioid use

2.0 Rationale

There is increasing evidence that an elective surgical event is often a patient's initial and greatest exposure to opioids.¹⁻³ In survivors of cancer surgery, persistent opioid use can be predicted by the dispensed amount of a patient's initial outpatient prescription at surgical discharge.^{1,4,5} Furthermore, national prescribing pattern data have shown that the initial outpatient prescription of *oral morphine equivalents (OME)* can be predicted by opioid utilization during the last 24hrs in the hospital.^{6,7} A tangible contribution from the surgical community would be the active implementation of a protocol to eliminate or reduce outpatient opioid dissemination in a

greater proportion of cancer survivors after oncologic surgery. In this context, we have implemented regional anesthetic techniques including ultrasound-guided four-point *bilateral quadratus lumborum (QL) block using 72-hr liposomal bupivacaine*. Despite the success of reducing our median length of stay from 10 days to 6 days with enhanced recovery protocols in 2016-17, only 5% of our patients were discharged without opioids after review of 158 consecutive pancreatectomy patients. Median initial outpatient prescription OME was 316mg, far above the 200mg OME recommended by the Centers for Disease Control.⁸ We thus see an opportunity to improve rapid postoperative opioid weaning to increase the proportion of opioid-free patients at surgical discharge. We hypothesize that a second, repeat QL block on postoperative day 4 will bridge the gap between the initial intraoperative QL block and ambulatory status, and increase the proportion of cancer survivors without postoperative outpatient opioid prescriptions. **Rescue blocks are currently used on an as-needed basis** only when the first block is insufficient or if the clinical team decides that the opioid use is subjectively too much. **We have not routinely used a 2nd block, because opioid-free discharge has never previously been a goal.** Our new goal is to **reduce dissemination of opioids into the community and reduce the risk of persistent opioid use among survivors.**

“Enhanced recovery after surgery,” or ERAS, is no longer a novel idea. However, its benefits are beginning to be seen beyond the early metrics of hospital stay and activities of daily living. Downstream benefits have included reduced complications, less readmissions (despite earlier discharges), less hospital resource consumption (cost), and improved postoperative quality of life. With the opioid epidemic increasingly discussed in both medical and lay literature, we are seeking to modify our enhanced recovery program in abdominal cancer surgery to reduce opioid exposure in the hospital. Medical literature has shown that oftentimes the first exposure or greatest exposure to opioids comes from an elective surgical event. Persistent opioid use (past 1yr) can be predicted by the size of a patient’s initial outpatient prescription **oral morphine equivalents (OME)**. And the **initial outpatient prescription OME can be predicted by the amount of opioids used in the last 24hrs of hospitalization**.

We recently analyzed 158 consecutive pancreatectomy patients’ opioid use by converting units into OME using an automatically generated download from our electronic health record. In our analysis, we found that intravenous patient-controlled anesthesia (IV-PCA) represented the largest contributor to total inpatient OME, even when universally paired with an ultrasound-guided regional anesthetic block with 72-hr liposomal bupivacaine. Median total OME (from all sources of pain control) for patients with IV-PCA was 525mg (range 28-4,362mg). Median OME contribution from IV-PCA alone was 373mg. **Only 5% of patients were discharged without opioids.** Median initial outpatient prescription OME was 316mg, far above the 200mg OME recommended by the CDC. We thus see an **opportunity to reduce opioid exposure** to increase the **proportion of opioid-free patients at discharge**. We are already embarking in improving our “usual care” enhanced surgical recovery bundle by using standardized non-narcotics and reducing initial IV-PCA settings.

HYPOTHESIS

- We hypothesize that a **second, repeat QL block on postoperative day 4** will bridge the gap between the initial intraoperative QL block and ambulatory status, facilitating a rapid opioid wean and **thus increase the proportion of cancer survivors without postoperative outpatient opioid prescriptions**. Ultimately, this should reduce dissemination of opioids into the community and reduce the risk of persistent opioid use in survivors.

3.0 Eligibility of Subjects

Inclusion:

- patients \geq 18 years of age undergoing elective open pancreatic resection for potentially curative intent (pancreaticoduodenectomy or distal pancreatectomy) who would otherwise be treated with QL block + IV-PCA converted to oral pain meds [non-narcotic bundle + opioid pain pill].

Exclusion:

- Patients with current or past substance [drug or alcohol] abuse disorder
- Laparoscopic or minimally invasive surgery

4.0 Research Plan and Methods

This is a **single-center phase II open-label randomized controlled trial** to assess the effect of an additional QL block on POD4 in patients undergoing pancreatic surgery with potentially curative intent. The primary endpoint is the proportion of patients who are **opioid-free on the discharge date**. Patients will be randomized with 1:1 ratio to receive either QL in OR + non-narc bundle +/- low-dose IV-PCA (control arm) or QL in OR and QL on POD4 AM + non-narc bundle +/- low-dose IV-PCA (experimental arm). The **allocation will be concealed until postoperative day 1** so that clinicians at the time of surgical consent will not be able to predict to which pathway the next enrollee will be assigned. Patients will be stratified based on pathway allocation (Green vs. Orange vs. Blue) and preoperative average daily OME use in the past 7 days (>5 mg vs. ≤ 5 mg OME).

Our **3 colored pathways are based on clinical predictors of pancreatic leak risk and thus median length of stay**. The median length of stay for Green (low-risk pancreaticoduodenectomy), Orange (high-risk pancreaticoduodenectomy), and Blue (distal pancreatectomy) patients is 6, 8, and 5 days, respectively. The length of stay affects the weaning, in that longer stays allow more time to wean off inpatient opioid use.

Method of Group Assignment and Randomization

Sequence Generation: Redcap will be used for 1:1 allocation with stratification for **postoperative pathway (Green, Orange, or Blue) which is determined preoperatively based on risk of pancreatic leak** and preoperative average daily OME use in the past 7 days (>5 mg vs. ≤ 5 mg OME).

Allocation Concealment and Mechanism: Allocation will be concealed at the time of enrollment from patients, providers, and researchers.

Implementation: Acute pain team, surgeons, advanced practice providers, fellows, and nurses will perform interventions and assessments per standard of care.

Blinding: All clinicians and patients will be **blinded from the allocation before surgery, intraoperatively, and until POD1**. The only difference in intervention will be the 2nd QL block which cannot be blinded.

Intervention Strategy:

On postoperative day 4 [at least 96hrs from initial QL on postoperative day “0”, which is the day of surgery, per FDA guidelines], patients will undergo a 2nd QL procedure in the regular hospital room by the Acute Pain Service attending anesthesiologist using ultrasound guidance, which is usual routine method. The intent will be to do the 2nd QL.

This will be a **Type I QL block**, which allows an anterior approach to the correct fascial layers. Using sterile technique, the attending anesthesiologist will guide the needle through the appropriate skin, subcutaneous, and muscle layers to find the right fascial plane **using ultrasound localization**. The risk of complications is virtually nil, because most hospital subcutaneous and intramuscular shots which are done blindly or by “landmark,” the QL block will be done by exact ultrasound guidance. **This block will only be done by Acute Pain Service certified attendings.** We are not studying this block’s mechanism or the drug’s mechanism – both of which are well documented in 1000’s of patients. **This RCT focuses on the novel timing of using this regional block to augment the opioid weaning process.**

Patients or providers may choose to forego the option if patients are already opioid-free or nearly opioid-free. If the patient is discharged before POD4, there will not be any 2nd injection. The **usual measures of non-narcotic bundle** [including acetaminophen, NSAIDs, muscle relaxers, and Lidocaine-secreting patches] and conversion from IV pain meds to oral pains will be done to reduce total opioid exposure and use.

The 2nd block is a “Rescue Block” which we currently utilized on the floor for patients with pain control that is not making the anticipated progress on postoperative day 4, and if we want to avoid opioids due to traditional issues like ileus, somnolence, and nausea. Thus, in terms of hospital billing, this is still within the realm of usual care. It is not experimental therapy.

There will be no sham procedure in the control arm. In other words, there will not be any subcutaneous injection of placebo drug in patients in the control arm, since this is a study of treatment sequencing rather than one focused on the drug itself. A sham procedure would be required if we were using an experimental drug in the intervention arm, but the analgesic effect of bupivacaine is well-proven already. We chose against a sham needle injection since the primary aim of this study focused on treatment sequencing with primary endpoint being opioid-free discharge. The “treatment” herein is the bundle of standardized non-narcotics and the clinical care that is typically given for weaning pain medications through an inpatient stay. The only difference between the 2 arms is that the “intervention” arm has the option (patient may refuse if they are already off opioids) for the rescue block while the “comparison/control” arm has to use usual measures to continue weaning opioids.

Pain measurement: Pain scores will be measured using usual care – visual analog scale by hospital inpatient nurses. They ask the patient every 4hrs on a scale 0-10, and this is documented in the EHR. Nurses then offer patients with symptomatic scores additional oral or IV pain meds as appropriate based on usual clinical care (IV if not eating or severe breakthrough pain) and oral if eating and pain is not urgent.

- **Liposomal bupivacaine – 72-hr action**
 - No repeat in 96 hrs per drug label
 - Rarely completely enough for pain control – often needs low-dose IV-PCA as well, but can reduce total opioid use if an opioid-sparing bundle is standardly used, which we will do (both arms get the same non-narcotic bundle in hospital and upon discharge).

- **Dosage instructions in Figure 3 below.** The Operating Room pharmacy has calculated the appropriate max dose of long-acting and short-acting bupivacaine which can be safely mixed. There are laminated placards in every operating room, and most nurses know the mixture by memory. Certainly the Acute Pain Service attendings do as well since they have performed 1000's of these injections in the past few years.
- **Liposomal bupivacaine has become our standard of care for open surgery.** We use this in 90% of our pancreas patients, while the other 10% get epidurals. There is extensive experience using liposomal bupivacaine for regional blocks. This RCT does not focus on the use of the block per se (since it is routine care), but rather the timing of it.

Comparison Strategy:

The control arm patients will have usual care with just the single QL using ultrasound guidance placed in the OR. When the liposomal bupivacaine wears off, **there will be no second QL**. The **usual measures of non-narcotic bundle** [including acetaminophen, NSAIDs, muscle relaxers, and Lidocaine-secreting patches] and conversion from IV pain meds to oral pains will be done to reduce total opioid exposure and use. Due to risk of harm from injection of placebo, there will not be any sham procedure

Decision on Discharge Opioid Prescription

To avoid bias in one arm or the other, all discharge prescriptions will be standardized. Both arms will get standard non-narcotic bundles of acetaminophen 650mg q6hrs, celecoxib 100mg q12hrs, and methocarbamol 250-500mg q8hrs. Slight dose variations can be allowed here based on pharmacy availability (e.g. recent national shortage of methocarbamol 500mg pills). To standardize the opioids, we will use a multiplier of 5 days x the last-24hrs opioid pill count. This can be found easily in the electronic health record. We chose 5 days because the CDC recommends 7 days max prescription and less than 200mg OME. All patients have clinic appointments within one week of discharge and have phone numbers to call if their multimodal pain management plan is insufficient. The chance of this is very low considering these patients are on the same plan on discharge as they have been in the last 24hrs in the hospital. The multiplier of objective opioid pain pill use will be more useful than the subjective pain score which varies from patient to patient in their interpretation of that "smiley-face" Likert scale.

Interim Analyses:

One interim analysis will be performed when half of the patients (N=53) have been randomized and received treatment. The trial will be stopped due to futility if the p-value is >0.774 for the primary endpoint.

Anticipated Results:

Participant Flow Diagram: see Figure 1

Recruitment

All patients meeting inclusion criteria above will be recruited from clinic either during the consultation meeting or during the preoperative meeting. Prior to these meetings, the patients may be sent a letter through MyChart (Appendix E) requesting permission to seek financial clearance in advance, to avoid delays should the patient agree to participate in the study.

Generalizability

The chosen regional block is a well-documented procedure in the anesthesia literature. The drug used in the block is universally available for other types of block. The non-narcotic

bundle consists of generic drugs with minimal costs and are all well within usual care guidelines. The postoperative care pathways are published and reproducible.

Potential Harms/Adverse Events:

- Because regional blocks with liposomal bupivacaine are standard of care and have been performed in 1000's of MD Anderson Cancer Center patients, there almost no clinically relevant adverse events that we anticipate besides the "trouble" of collecting the equipment, gathering the Acute Pain Service, and asking the patient to lie flat in bed for 30min on POD4. This is an extra procedure at bedside on POD4
- There could be pain and anticipatory anxiety for the bedside procedure
- Hematoma from needle sticks are possible but almost never seen
- There is the cost of the procedure which is a "rescue block," which we have used before for failed 1st time blocks. **We have just never used it as a supplemental block to wean patients completely off opioids, because being opioid-free has never been a priority.** The reality is that it is "easier" to just order oral opioids on POD4 and beyond rather than going to the "trouble" of doing a bedside procedure on POD4 to get a patient potentially opioid-free.
- Unblinded providers affecting discharge OME in one arm over another. We will minimize this using 2 methods to protect patients:
 - Standardized IV-PCA settings will be used starting in the recovery room immediately out of the operating room. Unless there is an allergy, we will use our standard medication, dilaudid 0.1mg IV q 10min as needed, with no basal dose. This can be adjusted based on clinical needs. This will be weaned off when the patient starts solid food diet.
 - Patients' daily pain scores (checked by nurses q4hr) will be used to ensure that adequate pain control prescribed before discharge. There is no "threshold" score that will be used since one patient's "4" is different than another patient's "4," but the trend will be useful to ensure patients are not being ignored. More importantly, all patients will be judged by their activities of daily living on the last 24hrs to ensure pain control is adequate.
 - **The number of opioid pills will be formulaic to avoid bias by clinicians or patients in one arm or the other - we will take the last 24hrs of inpatient opioid pills used and multiply by a factor of 5 days to make this number standardized between the 2 arms.**
 - **Both arms get the same non-narcotic pain management bundle for inpatient and discharge.**
- **Prospective AE Records**
 - Inpatient advanced practice providers (nurse practitioner or physician assistant) will document complications daily prospectively
 - **Hospitalization, 30-day, and 90-day complications prospectively recorded** into our Pancreas Surgery Database RCR01-112 systematically on a weekly basis with faculty attendance
 - **We record all complications for 90 days after all operations using our faculty-led weekly review. Therefore we plan to ask for DSMB waiver since we are not doing any experimental procedure or using any new drug.**
- **Safety Review**
 - If the analysis of the first 20 patients yields complication rates from the intervention arm above the *pre-determined acceptable level*, the study will be terminated. This level is at least 25% of patients requiring deviation from their usual pathway and anticipated stay.

[figure not shown]

Figure 2. Study intervention timeline

| | Pre- Op Days | Inpatient Postop Day | | | | | | | | | | | Outpatient Month ^{a, b} | | | |
|------------------------------------|--------------------|----------------------|-------------|---|---|---|---|---|---|---|----------------|----|-------------------------------------|---|---|----|
| | | -30 to 0 | PACU "0" | 1 | 2 | 3 | 4 | 5 | 6 | 7 | 8 | DC | 1 | 3 | 6 | 12 |
| Oral Morphine Equivalents | X | X | X | X | X | X | X | X | X | X | X | X | X | X | X | X |
| MDASI-GI | X | | | | | X | | | | | X ^c | X | | X | X | |
| Pain Score | X | X | X | X | X | X | X | X | X | X | X | | | | | |
| Hospital Cost | | | | | | | | | | | X | | | | | |
| Adjuvant Therapy [if needed] | | | | | | | | | | | | X | | X | X | |
| Informed Consent | X | | | | | | | | | | | | | | | |

Median Length of Stay is 5 days for Blue Pathway, 6 for Green, and 7 for Orange Pathways.

Day of surgery is called postoperative day “0” and the 1st day after surgery is called postop day 1. This is different than medical terminology in which the “count” of hospital days starts at “1,” not “0” as with surgery.

[figure not shown]
- +- 1 week for outpatient follow up.
- Survey may be administered via phone, email, or in clinic.

c. Survey may be administered from day of discharge to the first post-OP visit via phone, email, or in clinic.

Figure 3. Liposomal bupivacaine mixture recommendations from OR Pharmacy [approved 2 years ago].

When mixing Bupivacaine HCl with Exparel, do not exceed a 1:2 ratio of Bupivacaine HCl:Exparel. The maximum 1:2 ratio is 150 mg Bupivacaine HCl:266 mg Exparel.

Below are the maximum 0.5% and 0.25% Bupivacaine HCl amounts when mixing with Exparel:

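### The arm definition's morning slot for the second block cannot meet the protocol's own 96-hour minimum when the first block was placed after noon on the day of surgery

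*Combined protocol and SAP*

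**What the plan says.** Section 4.0 (Research Plan and Methods) states the timing of the second block in three places.

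- The opening paragraph, which defines the randomized arms, gives the experimental arm as "QL in OR and QL on POD4 AM".
- Intervention Strategy places the block as follows: "On postoperative day 4 [at least 96hrs from initial QL on postoperative day" 0. It attributes the interval to FDA guidelines and does not mention the morning.
- The liposomal bupivacaine bullets under Intervention Strategy say "No repeat in 96 hrs per drug label".

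The notes under Figure 2 fix the day count: the day of surgery is day 0, "and the 1st day after surgery is called postop day 1".

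For the first block, the text gives only a place. Comparison Strategy describes "usual care with just the single QL using ultrasound guidance placed in the OR". No clock time, no position within the operation and no restriction to morning cases is stated.

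**The concern.** The arm definition and the minimum interval both apply to the same procedure, and for some first-block times they exclude each other. No sentence says which prevails.

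Three things are at stake. First, Section 4.0 presents the trial as a study of when the block is given rather than of the block or the drug, so the timing is the intervention and should be stated once. Second, the interval is the protocol's own limit on repeat dosing, and anyone scheduling from the arm definition alone could fall inside it. Third, adherence has no single standard. After an afternoon first block, a second block on the afternoon of day 4 meets Intervention Strategy but departs from the arm definition, and a morning block does the reverse.

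**Working it through.** **Inputs**
- Second block: morning of day 4 (Section 4.0, arm definition). AM is read as before 12:00.
- Minimum interval: 96 h (Section 4.0, Intervention Strategy and drug bullets).
- Day of surgery = day 0 (notes under Figure 2).
- First-block clock time *t* on day 0: not in the documents, so it is varied below.

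**Step 1. Is the Intervention Strategy wording consistent by itself?** From time *t* on day 0 to time *t* on day 4 is 4 × 24 = 96 h. The second block is therefore permitted from time *t* on day 4 until the end of that day. Some permitted time on day 4 exists for any *t*, so this wording holds together.

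**Step 2. Add the morning condition.** The second block must now fall between *t* and 12:00 on day 4, a window of 12:00 − *t*.

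| First block, day 0 | Earliest permitted time, day 4 | Morning time left |
|---|---|---|
| 08:00 | 08:00 | 4 h |
| 10:00 | 10:00 | 2 h |
| 11:00 | 11:00 | 1 h |
| 12:00 | 12:00 | 0 h |
| 14:00 | 14:00 | none |
| 16:00 | 16:00 | none |

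The window shrinks to nothing at noon. For any later *t*, the two conditions cannot both be met.

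**Step 3. Size of the shortfall.** With the second block at clock time *s* on day 4, interval = 96 h + (*s* − *t*). Take the latest morning minute, *s* = 11:59 (11.98 h), which is the most favourable case:
- *t* = 13:00: 96 + 11.98 − 13 = 94.98, about 95 h
- *t* = 14:00: 96 + 11.98 − 14 = 93.98, about 94 h
- *t* = 16:00: 96 + 11.98 − 16 = 91.98, about 92 h

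All are below 96 h, and an earlier morning slot would lower them further.

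**Step 4. Does it reach the statistics?** The calculation in Section 5.0 uses 5% versus 25% opioid-free, 53 per arm, a two-sided 5% level and 10% dropout. None of these depends on the hour of the second block, and neither does the chi-squared test.

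**The case against.** The best defence is that the two statements do not carry equal weight. AM appears once, in a one-sentence summary of the arms. The text that describes how the block is given omits it, and the 96-hour minimum is stated twice and attributed to an outside authority. Staff who read the whole section would not be led into an early dose. This largely stands: a reader might infer that the protocol directs dosing inside its own limit, and the documents do not support that. What remains is that no sentence gives either statement precedence. If staff do observe the 96 hours after an afternoon first block, the arm is not delivered as defined.

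Two other stronger readings also fail.

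- A reader might infer that most morning first blocks are affected too, by fixing the second block at an early hour. With 08:00 assumed, a first block at 10:00 gives 94 h. But 08:00 appears nowhere in the documents, and a second block between 10:00 and noon would satisfy both conditions.
- A reader might infer that moving the block later on day 4 changes which short-stay patients receive it. The documents give a median stay of 5 days for the Blue pathway and say that patients who leave before day 4 get no second block. They give no figure for discharges during day 4, so this effect is neither shown nor measurable from the plan.

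**Conclusion.** The contradiction is real but narrow, and its severity is minor. It exists only for first blocks placed after noon, and it comes from the word AM alone. For morning first blocks the two conditions are compatible within a window that closes at noon.

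In the afternoon examples above, the shortfall against 96 h is about 1 to 4 hours at best. The share of patients affected is unknown: 0% if every first block is placed in the morning, 100% if every one is placed after noon. The conclusion assumes that AM means before noon and that the Figure 2 day count applies throughout.

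The point bears on how the intervention is defined and how adherence is judged. It does not bear on sample size, power or the primary comparison.

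**What to change.** Reconcile the arm definition, Intervention Strategy and the drug bullets in Section 4.0 into one timing statement for the second block, and use it wherever the arm is described. Which statement should stand is a clinical decision for the sponsor, and this review does not propose one.

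Record the clock time of both blocks for every experimental-arm patient who receives the second one, so that the interval and adherence can be verified.

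The cost is a wording change and two recorded times per patient. The documents place pain scores and opioid counts in the electronic health record but do not say whether block times are there, so the sponsor should confirm the source rather than assume it.

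### Allocation is revealed on POD1, three days before the arms can differ; keeping it hidden until POD3 evening or POD4 morning would remove avoidable arm knowledge at little cost

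*Combined protocol and SAP*

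**What the plan says.** All places are in the combined protocol and SAP.

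- **Concealment.** Section 4.0 states that the "allocation will be concealed until postoperative day 1". The reason given is that clinicians should not be able to predict the next assignment at surgical consent. The Blinding paragraph covers patients and clinicians, and ends their blinding on POD1.
- **Where the arms differ.** "The only difference in intervention will be the 2nd QL block which cannot be blinded". That block is given on the morning of POD4, at least 96 hours after the first. There is no sham.
- **Who may go without the block.** Under Intervention Strategy: "Patients or providers may choose to forego the option if patients are already opioid-free or nearly opioid-free", and "If the patient is discharged before POD4, there will not be any 2nd injection".
- **Time in hospital.** "The median length of stay for Green (low-risk pancreaticoduodenectomy), Orange (high-risk pancreaticoduodenectomy), and Blue (distal pancreatectomy) patients is 6, 8, and 5 days, respectively". A note under Figure 2 gives 7 days for Orange.
- **Acknowledged risk.** Potential Harms/Adverse Events lists "Unblinded providers affecting discharge OME in one arm over another". The remedies are standard starting PCA settings, of which the plan says "This can be adjusted based on clinical needs", and a formula for the discharge prescription: "we will use a multiplier of 5 days x the last-24hrs opioid pill count".
- **Outcomes.** The primary outcome is the proportion with no opioid on the discharge prescription. Total OME in hospital is a secondary outcome (section 1.0).

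**The concern.** Concealing the allocation until after consent protects enrolment. That purpose is equally served by a reveal on POD1, POD3 or POD4, and the plan gives no reason for choosing POD1. From POD1 to the morning of POD4 both arms are meant to receive the same care, but patients, nurses and prescribers know who is due a second block. They also control what is being measured: the PCA can be changed, and nurses offer additional oral or intravenous drug according to pain score.

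Two things are directly exposed. Total inpatient OME counts the opioids given on those days. And the decision to forego the block depends on being opioid-free or nearly so, a state reached while the arm is known. A team expecting a block on POD4 might wean less hard beforehand, or harder; the direction cannot be told from the documents. Arm knowledge after POD4 cannot be avoided without a sham. Arm knowledge before POD4 can.

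**Working it through.** **1. Length of the avoidable period.** Reveal on POD1, block on POD4: 4 − 1 = 3 days.

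**2. Share of the arm-known stay.** Take discharge on the POD equal to the median stay, so arm-known days = median stay − 1.

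| Pathway | Median stay | Arm-known days | Share before the block |
|---|---|---|---|
| Blue | 5 | 4 | 3/4 = 75% |
| Green | 6 | 5 | 3/5 = 60% |
| Orange (section 4.0) | 8 | 7 | 3/7 = 43% |
| Orange (Figure 2 note) | 7 | 6 | 3/6 = 50% |

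These shares describe exposure over the stay, which is what matters for total inpatient OME. They do not describe exposure of the primary endpoint.

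**3. Exposure of the primary endpoint.** The discharge prescription is set by pills used in the last 24 hours. At the median stays that window opens at about 5 − 1 = POD4 (Blue), 6 − 1 = POD5 (Green) and 8 − 1 = POD7 or 7 − 1 = POD6 (Orange). It therefore lies at or after the block, when arm knowledge is unavoidable. Knowledge from POD1 to POD4 reaches it only by carry-over of the earlier weaning course, or through the decision to forego the block. The exception is a patient who leaves on POD4 or sooner, whose window opens before the block. The documents do not say how many there are.

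**4. What the formula protects.** Prescription = 5 × last-24-hour pill count. Since 5 × 0 = 0 and 5 × any positive count is positive, the binary endpoint turns on whether the count is zero. The formula removes discretion at the prescribing step. It leaves the inpatient use that produces the count as it was.

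**5. Is power at stake?** Inputs from section 5.0: 5% against 25%, 53 per arm, two-sided 5% chi-squared test, stated power 84.5%. Reproduction: pooled normal approximation 83.2%, unpooled 85.2%, exact enumeration of the uncorrected test 85.9%, simulation with the p > 0.774 futility stop 85.4%. Enrolment: 106/0.9 = 117.8, so 118. The plan's figures reproduce.

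Now compare the plan with randomising on POD4 only those who would get the block, from the same 106 consented. The documents give no untreated share *u*, so the values below are assumptions. Let *q* be the opioid-free proportion among the untreated and *b* the benefit among the treated.

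- As written: n = 53 per arm, 0.05 against 0.05 + (1 − u)b.
- POD4 randomisation: n = floor(53(1 − u)), p0 = (0.05 − uq)/(1 − u) against p0 + b.
- Reading A: the 25% is the rate in the whole experimental arm, so b = 0.20/(1 − u). Reading B: the 25% applies only to those who get the block, so b = 0.20.

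Exact power with q = 0.05 and no futility stop:

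| u | n per arm, POD4 | A: as written | A: POD4 | B: as written | B: POD4 |
|---|---|---|---|---|---|
| 2% | 51 | 85.9% | 85.5% | 84.8% | 84.4% |
| 5% | 50 | 85.9% | 87.9% | 83.0% | 85.2% |
| 10% | 47 | 85.9% | 88.6% | 79.7% | 83.1% |
| 20% | 42 | 85.9% | 90.4% | 72.0% | 78.4% |

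With q from 0 to 0.10 and both readings, the gain from moving randomisation is −0.7 to −0.1 points at u = 2%, 1.4 to 2.9 at 5%, 1.4 to 5.0 at 10%, and 2.1 to 10.8 at 20%. The negative sign at 2% comes from rounding the arm size down.

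**6. Recruitment if randomisation moved.** At u = 20%, keeping 106 randomised needs 106/0.8 = 132.5, so 133 consented. That leaves 140 − 133 = 7 of the screening limit for screen failures and aborted surgery.

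**The case against.** The strongest reply has three parts.

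*The decisive window is untouched.* At the median stays the primary endpoint is settled after the block, when the arm is known whatever is done. This stands. A reader might infer from the 75%, 60% and 43% shares that most of the primary endpoint's exposure is avoidable. Step 3 shows that it is not.

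*There may be a reason for POD1.* The block needs a certified attending, equipment and a bedside slot, so early notice helps planning. The plan's silence does not prove that no reason exists. But no reason is stated, and section 2.0 says that the same kind of block is already given as needed, so short notice looks workable.

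*Untreated patients in the experimental arm are part of the strategy.* Section 4.0 describes that arm as having the option of a block and says in advance who may go without. This also stands. A reader might infer that the trial is underpowered by dilution and must randomise on POD4. The documents do not support that: they give no untreated share, and section 5.0 most naturally states 25% as the experimental arm's rate, which already allows for skipped blocks. Power falls below 84.5% only under Reading B with an assumed share of 5% or more. Much larger losses can be produced by assuming that most untreated patients are opioid-free in both arms. At 20% untreated with 95% opioid-free, however, the control rate becomes 0.20 × 0.95 + 0.80 × 0.05 = 23%, which contradicts the planned 5%.

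**Conclusion.** The point holds for the timing of the reveal. Three days of arm knowledge precede any treatment difference, and the stated purpose of concealment does not need them. They directly expose total inpatient OME and the state that governs foregoing the block. At the median stays they expose the primary endpoint only indirectly. No bias can be quantified from the documents, in size or direction, so this is an inexpensive improvement and not a demonstrated flaw in the primary result.

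The as-randomised comparison is valid for the offer of a block, and no shortfall from 84.5% is shown. Moving randomisation to POD4 among those who would be given the block is a legitimate alternative, but it answers a question about a narrower population. Its gain ranges from nil to a few points at assumed untreated shares of 2% to 10%, and is larger only if the share is nearer 20%. It is not a required correction. The day counts assume discharge at the median stay.

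**What to change.** Amend the concealment and Blinding text of section 4.0 so that allocation stays hidden from patients and clinicians until the evening of POD3 or the morning of POD4. Before the reveal, record for each patient still in hospital whether patient and provider would want the block, with the reason if not. Keep randomisation, the strata, 53 per arm, and the analysis of all randomised patients as randomised. Patients discharged before the reveal stay in that analysis.

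The cost is an amendment, a short form, a later release of the allocation from REDCap, and shorter notice for the Acute Pain Service. Arm knowledge after POD4 remains. The recorded intentions also supply, in both arms, the untreated share that the plan now lacks.

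If the sponsor prefers the effect among patients who would be given the block, randomisation could instead move to POD4. The control rate would then need re-estimating for that population, and the limit of 140 screened would need revisiting.
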